All patients enrolled in the study must have an injury that requires wear of a CAM walker boot for at least six weeks and have ambulation ad libitum without other aids (e.g. crutches, canes, scooters, wheelchairs, etc.). Patients will be excluded from the study if they are a recent post-operative patient for lower extremity injury, have an additional acute injury to a lower extremity or back other than the foot or ankle injury being treated by the CAM walker boot at the time of initiation of treatment, have an ongoing or history of lower extremity joint injury, arthritis, or back pain or have restricted weightbearing as instructed by a physician (i.e. for ankle fracture that cannot weight bear). Additionally, pregnant women and non-English speaking patients will not be eligible for this study.

IV. Subject Enrollment

Subjects will be included in this study if they are eligible to receive treatment with a CAM walker boot for a nonoperative ankle fracture, for a period of at least six weeks. Once the patient is deemed eligible for the study because of their injury, the physician will ask if the patient is interested in hearing more regarding the research study we are conducting. If the patient agrees, the study staff will explain in depth the study aims and protocol during the office visit. At this time, the study staff will consent the patient, and it will be made clear that the patient will be able to rescind their participation at any time during the study for any reason, and that this will not impact their continued care at the Brigham Foot and Ankle Clinic. Brigham Foot and Ankle physicians will be available for any additional questions if needed. The study staff will stress that the study is voluntary, provide all information regarding alternate treatment options, and remind patients that even if they do consent, they will have the opportunity to withdraw participation at any time for any reason. Any subjects who agree to participate will then be asked to fill out questionnaires as a means to obtain initial data.

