All patients who consent will be randomly divided into two equal sized groups (n=50) — Group I and Group II. We will randomize our patients using a random number generator. Group I will be randomized to receive CAM walker boot treatment and Group II will receive CAM walker boot treatment with the EVENup orthotic shoe lift as an intervention. Cross-over will not be explicitly offered between the groups, but if participants in Group I utilize an orthotic shoe lift of their own volition, this will be documented. All participants will be evaluated using an intention-to-treat (ITT) approach, where each subject will be analyzed according to their randomization assignment, regardless of actual treatment received.

V. Study Procedures

Initial Visits:

Initial data taken for all patients at the time of enrollment will include demographics (age, sex, race, medical co-morbidities, medications, BMI, smoking history), injury or diagnosis being treated, history of lower extremity pain or low back pain (i.e. hip, knee, back pain), history of lower extremity or low back surgery or injury (i.e. hip or knee replacement, prior fracture) and functional outcome scores using the following surveys:

- Foot and Ankle Ability Measure (FAAM) pertaining to the injured foot or ankle
- Visual Analog Scale (VAS) of pain for each lower extremity joint or low back (low back, right / left hip, knee, ankle, foot, other)

Patients in Group I will be assigned to receive a course of CAM walker boot treatment for a period of six weeks.

Patients in Group II will be assigned to receive a course of CAM walker boot treatment with an EVENup orthotic shoe lift to be worn on the contralateral foot for a period of six weeks.

The opportunity for crossover from Group I to Group II will be permitted if patients develop severe pain. These patients can attempt to remediate their pain by using an EVENup orthotic shoe lift, which are readily available for their purchase in a variety of settings.

Follow Up Assessments:

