We will prospectively identify patients who have been diagnosed with nonoperative ankle fractures that require CAM walker boot treatment, at the previously stated clinic sites. Through a one-sided power analysis, with an alpha = 0.05 and 80% power, we determined that a minimum of 42 participants would be needed to be enrolled in each group to detect a 40% reduction in CAM walker-boot associated pain, compared with a previously reported occurrence of associated pain in 67% of patients.⁶ For this reason, we aim to enroll 100 patients in this study, with 50 patients in each of the two arms. Any patients over the age of 18, regardless of gender or ethnicity, who fit the previously stated criteria will be recruited. The study will end after 100 subjects are enrolled.

The primary outcome measurements will be the change in VAS of pain at secondary sites and FAAM from the start of prescribed treatment to six weeks after initiation of bootwear. Our secondary outcome measurements will be the change VAS of pain at secondary sites and FAAM at twelve weeks after initiation of the boot, and at twenty four weeks after initiation of the boot. We will use an ITT approach, where each subject will be analyzed according to their randomization assignment, regardless of actual treatment received. We will use a t-test to compare change in outcome measurements between the two arms.

Patient responses to the VAS and FAAM forms will be collected via REDCap. All statistical analysis and data accumulation will be performed using Microsoft Excel (Microsoft Corporation, Redmond, WA). This includes means, ranges, SD and percentiles.

VII. Risks and Discomforts

Risks to the subject are very minimal. Because this is a prospective study, there is a risk of noncompliance by the patients, for which reason patient cooperation is important. Risks of CAM walker boot wear include the potential for delayed recovery and/or re-injury. There is also previously reported risk of CAM walker boot-associated pain⁶, which we aim to study the reduction or elimination of in this RCT. Additionally, the EVENup orthotic shoe lift increases the elevation of the foot contralateral to the CAM walker boot, although this should not impart any additional risk to patients.

VIII. Potential Benefits

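### The t-tests on change use only patients with that visit's score and no missing-data method is given, so weeks 12 and 24 can be biased if loss relates to pain differently in the two arms

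*Combined protocol and SAP*

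**What the plan says.** Section VI makes the change in VAS pain at secondary sites and in FAAM to week 6 the primary outcomes, with the same measures at weeks 12 and 24 as secondary. The comparison is a single sentence: "We will use a t-test to compare change in outcome measurements between the two arms". The software is equally brief: "All statistical analysis and data accumulation will be performed using Microsoft Excel".

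On who is analysed, section IV says: "All participants will be evaluated using an intention-to-treat (ITT) approach". Sections IV and VI both explain this as analysis by randomised arm, whatever treatment was actually received.

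On loss of data:
- Section IV tells participants that "the patient will be able to rescind their participation at any time during the study for any reason".
- Section V lets surveys be completed at home through an emailed link, and sets no clinic visit for all patients after week 6.
- Section V also takes out of the study those patients whose fracture has not healed and who are moved to another treatment.

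The plan says nothing on missing scores, imputation, repeated-measures modelling or sensitivity analysis.

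**The concern.** A two-sample t-test on change cannot use a patient who lacks either score. Each visit is therefore analysed on the cases available at that visit, and the set may differ from visit to visit and from the set randomised. The test at week 24 also ignores the week-6 and week-12 scores of a patient who later stopped responding, although those scores carry information about the missing one.

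Weeks 12 and 24 are the most exposed. Withdrawals accumulate, remote completion is likelier, and the removal of non-healed patients takes effect after the six-week visit. These visits also carry the part of Aim 2 about pain that persists after the boot comes off. Patients know whether they have a lift, so loss that depends on pain differently in the two arms is plausible. Enrolling more patients than the calculated minimum protects precision but not against this bias.

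**Working it through.** **1. The plan's own sample size and its margin.** Inputs from section VI: "Through a one-sided power analysis, with an alpha = 0.05 and 80% power"; "previously reported occurrence of associated pain in 67% of patients"; "to detect a 40% reduction in CAM walker-boot associated pain". Read as a relative reduction, the Group II rate is 0.67 × 0.60 = 0.402, the difference is 0.268 and the mean rate is 0.536.

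n = [1.645·√(2 × 0.536 × 0.464) + 0.842·√(0.67 × 0.33 + 0.402 × 0.598)]² / 0.268² = 41.8, so 42. This matches "a minimum of 42 participants would be needed to be enrolled in each group".

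Enrolling 50 allows for 1 − 42/50 = 16% loss. One-sided power for this contrast is 86.0% with 50 per arm, 80.2% with 42 and 78.4% with 40 (20% loss). The margin covers lost precision only.

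**2. Direction of bias, on the plan's planning rates.** Expected numbers with pain are 0.67 × 50 = 33.5 in Group I and 0.402 × 50 = 20.1 in Group II. Suppose 8 patients with pain are missing.

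| Missing patients, all with pain | Group I observed | Group II observed | Difference (true 26.8 points) |
|---|---|---|---|
| 8 in Group I only | (33.5 − 8)/42 = 60.7% | 40.2% | 20.5 |
| 8 in each arm | 60.7% | (20.1 − 8)/42 = 28.8% | 31.9 |

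The benefit is understated in the first row and overstated in the second. Equal numbers lost are not the same relation to pain: 8/33.5 = 24% of Group I patients with pain are lost, against 8/20.1 = 40% in Group II. The pain rate is the planning quantity, not the analysed change score, so this table shows direction only.

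**3. Size of bias at week 24, on assumed values.** None of these inputs is in the documents: SD 2.4 on a 0-10 VAS, correlation 0.30 between baseline and follow-up, correlation 0.49 or 0.70 between weeks 6 and 24, true difference 0.50, 16% or 20% lost after week 6. Loss depends on week-6 pain in Group I only, through a logistic model with slope 0.5 to 3 per SD.

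Let k be the amount, in SD units, by which the mean week-6 score of the remaining Group I patients falls below that of the whole arm. The t-test on change is then shifted by

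SD × (correlation of weeks 6 and 24 − correlation of baseline and week 6) × k.

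Over these settings k runs from about 0.077 to 0.30.

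- Mildest case: 2.4 × (0.49 − 0.30) × 0.077 = 0.035, so the t-test gives about 0.47.
- Strongest case: 2.4 × (0.70 − 0.30) × 0.30 = 0.29, so it gives about 0.21.

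Simulation agrees. An estimate that also uses baseline and week-6 scores gives 0.49 to 0.51 throughout. With the same dependence and equal loss rates in both arms, the t-test gives about 0.50. With the dependence in Group II only, the shift changes sign, giving about 0.53 to 0.79.

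The shift does not depend on the true difference, so its share does. At correlation 0.49, 20% loss and slope 3 it is 2.4 × 0.19 × 0.30 = 0.14. The t-test gives 0.36 for a true 0.50 but 0.86 for a true 1.00.

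**4. When loss depends on the unseen score itself.** Assume SD of change 2, true difference −1.00 and 13-22% missing per arm. The t-test gives −1.00 if loss is unrelated to pain, about −0.90 if the dependence on the score is the same in both arms, and −0.67 to −0.50 if it is in Group I only. A model that assumes data are missing at random does not remove this bias. It is the relevant case for patients with no score after baseline.

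**The case against.** Several points on the other side are sound.

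- **Intention-to-treat.** A reader might infer that the plan contradicts its own promise. It does not. Sections IV and VI define the term by assigned arm and treatment received, which deals with crossover and not with missing outcomes. The statement that all participants are evaluated shows the intent, but the plan is silent rather than inconsistent.
- **Completers.** A reader might call this a completers' analysis. Each test uses the cases available at its own visit, so a patient missing week 24 still counts at week 6.
- **Pain-driven dropout.** A reader might infer that Group I patients in pain will leave and that the lift's benefit will be understated. No section documents such dropout. Section V lets Group I patients with severe pain use a lift, and nothing removes them from follow-up. The direction is not fixed either, as the table shows.
- **The primary endpoint.** Week 6 has a clinic visit for everyone, and a mixed model adds little for a patient with no score after baseline. The modelling gain is mainly at the secondary visits.
- **The illustration.** The largest shifts come from loss related to pain in one arm only, and their share of the effect depends on the assumed 0.50.

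What remains is that the stated test cannot use a patient without that visit's score and that nothing in the plan supplies a method. The one loss written into the protocol, removal of non-healed patients moved to other treatment, is linked to clinical outcome and falls on weeks 12 and 24.

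**Conclusion.** The concern holds as a gap in method with a risk of bias, not as a demonstrated bias. The analysis as written uses available cases at each visit, with no missing-data method and no sensitivity analysis. Bias at weeks 12 and 24 requires loss related to pain differently in the two arms, and it can go either way. On the assumed values with loss related to pain in Group I only, the t-test returns about 0.21 to 0.47 for a true 0.50 while a longitudinal estimate returns about 0.50. With the same dependence at similar rates in both arms, or loss unrelated to pain, bias is small. These sizes rest on an assumed SD, correlations, loss rates and dependence, because the documents give none of them. At week 6 the exposure is probably smaller, and it calls for sensitivity analysis more than for a different model.

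**What to change.** In section VI, for each defined outcome score, replace the separate t-tests with one linear mixed model for repeated measures on all randomised patients: weeks 0, 6, 12 and 24, arm by visit, a common baseline mean and unstructured covariance. Take the week-6 contrast as primary and the week-12 and week-24 contrasts as secondary from the same fit. Multiple imputation using all visits is an acceptable equivalent. The plan must first say how the several VAS sites form the score or scores to be modelled.

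Add a sensitivity analysis, such as a tipping-point analysis, that varies the missing scores in each arm separately until the conclusion changes. This is the main safeguard at week 6.

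State in section V that surveys at weeks 12 and 24 continue to be collected from patients moved to alternative treatment. This concerns data collection only, not their care.

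Run the analysis from a saved script in software that fits such models; Excel has no built-in mixed model.

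The cost is a few sentences, a change of software, a slightly more complex analysis and a missing-at-random assumption, which the sensitivity analysis probes. No extra patients or visits are needed, but surveys must be obtained from patients who would otherwise have left the study.

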With regard to clinic visits, all patients in Groups I and II will be seen in the clinic at six weeks to assess the outcomes of the prescribed treatments. Visits will occur at any of the previously mentioned clinic sites. If the fracture has not completely healed, previously prescribed treatment may be extended until healing has been deemed achieved at subsequent follow up visits. Total duration of the prescribed treatment will be recorded for each patient. Additionally, alternative treatment options may be utilized at the physician's discretion if healing has not been achieved with a CAM walker boot. This cohort of patients will not further progress in the study.

Outcomes:

Outcomes for both Group I and Group II will be taken at initiation of boot wear, at six weeks after initiation of the boot, at twelve weeks after initiation of the boot, and at twenty-four weeks after initiation of the boot. We will use the following surveys to measure the outcomes of our patients:

- Foot and Ankle Ability Measure (FAAM) pertaining to the injured foot or ankle
- VAS of pain for each lower extremity joint or low back (low back, right / left hip, knee, ankle, foot, other)

Initial data and all outcome scores will be obtained from subjects using the web-based Partners affiliated Research Electronic Data Capture (REDCap) (Vanderbilt University, Nashville, TN). Use of REDCap will either be done in person on Partners approved devices with the guidance of study staff, or from home using an email-based system of delivery. The latter will require the obtaining of email addresses from subjects and the sending of encrypted study materials securely with the 'send secure' function. Participants can also receive unencrypted emails if they acknowledge the risks, and that Partners will not be held responsible.

VI. Biostatistical Analysis

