There is no additional benefit to participants in Group I, as they will receive the standard course of CAM walker boot treatment. Potential benefits for participants in Group II include the reduction or prevention of the occurrence of pain, particularly contralateral or ipsilateral lower extremity joint pain or low back pain, due to the simulated LLD compensation provided by the EVENup orthotic shoe lift. If a clinically significant difference is found to exist between treatment arms within this study, these results will guide our future clinical practice in recommending orthotic shoe lifts to patients receiving CAM walker boot treatment.

IX. Monitoring and Quality

The study is not expected to affect the safety of any subjects involved. In order to ensure the safety of subjects, the principal investigator will review all outcome data at the standard follow-up visits and record any adverse events. If adverse events occur, the principal investigator will review the reasonable cause for the event and determine if the research should be altered or stopped.

All data will be collected, viewed, recorded, and analyzed only by study staff listed. The VAS and FAAM measures that the patients will complete at initial visit, six weeks after initiation of the boot, twelve weeks after initiation of the boot, and twenty-four weeks after initiation of the boot data will be recorded in the REDCap database and will be stored on password-protected Partners computers. Only study staff will have access to the digital database.

X. References

2. Preferred Management of Recalcitrant Plantar Fasciitis Among Orthopaedic Foot and Ankle Surgeons - Benedict F. DiGiovanni, Andrew M. Moore, Jason P. Zlotnicki, Stephen J. Pinney, 2012. https://journals.sagepub.com/doi/abs/10.3113/FAI.2012.0507?rfr_dat=cr_pub%3Dpubmed&url_ver=Z39.88-

2003&rfr_id=ori%3Arid%3Acrossref.org&journalCode=faib. Accessed July 30, 2019.

3. Surgery for Type B Ankle Fracture Treatment: a Combined Randomised and Observational Study (CROSSBAT) | BMJ Open. <https://bmjopen.bmj.com/content/7/3/e013298.long>. Accessed July 30, 2019.
4. Tendinopathies of the Foot and Ankle - American Family Physician. <https://www.aafp.org/afp/2009/1115/p1107.html>. Accessed July 30, 2019.

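### Non-pain harms are not solicited, have no stated recording route after week 6 in healed patients and are not compared by arm, so they may be under-recorded

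*Combined protocol and SAP*

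**What the plan says.** All references are to the combined protocol and SAP.

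- **Recording rule.** Section IX (Monitoring and Quality) states that "the principal investigator will review all outcome data at the standard follow-up visits and record any adverse events". The investigator then considers the cause of any event and whether the research should be altered or stopped.
- **Visits.** Section V (Follow Up Assessments) states that "all patients in Groups I and II will be seen in the clinic at six weeks to assess the outcomes of the prescribed treatments". Later visits appear only for incomplete healing: "previously prescribed treatment may be extended until healing has been deemed achieved at subsequent follow up visits". Patients moved to alternative treatment for non-healing do not continue in the study.
- **Surveys.** Section V (Outcomes) collects the FAAM and the VAS at the start of boot wear, at six weeks, "at twelve weeks after initiation of the boot, and at twenty-four weeks after initiation of the boot". They are completed in person with study staff "or from home using an email-based system of delivery". The pain instrument is a "VAS of pain for each lower extremity joint or low back (low back, right / left hip, knee, ankle, foot, other"). The FAAM refers to the injured foot or ankle.
- **Other relevant data.** Section V records total treatment duration for each patient.
- **Risk and use of results.** Section VII names delayed recovery and re-injury as risks of the boot. Of the raised contralateral foot it says "although this should not impart any additional risk to patients". Section VIII says that a clinically significant difference between arms, if found, will guide recommending lifts.

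**The concern.** The plan measures pain carefully and leaves other harms to whatever comes to light at a visit. A device that raises one foot could plausibly affect falls or new injuries, in either direction, and a patient may stop wearing it because of a problem. None of these is the subject of a stated question.

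Two things are at stake. First, the alter-or-stop review in Section IX can act only on events that reach the investigator, and no contact is scheduled between enrolment and week 6, when planned lift wear ends. Second, if the trial leads to a recommendation for the lift, that recommendation would rest on pain and function scores, with little systematic information on other harms in either arm.

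**Working it through.** **1. The plan's own figure.** The documents give no adverse-event rate or detection target. Their one computed figure is 42 per group (Section VI). It follows from the one-sided pooled two-proportion formula with p1 = 0.67 and p2 = 0.67 × 0.60 = 0.402:

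n = [1.645·√(2 × 0.536 × 0.464) + 0.842·√(0.67 × 0.33 + 0.402 × 0.598)]² / 0.268² ≈ 41.8, so 42.

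The figure reproduces and this point does not affect it.

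**2. Scheduled contacts after baseline.** There is one clinic visit for all patients (week 6) and three survey times (weeks 6, 12 and 24). A patient healed at week 6 has no further clinic visit stated.

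**3. What each kind of harm can be recorded by.**

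| Harm | Planned wear, to week 6 | After week 6, healed patient | Planned comparison by arm |
|---|---|---|---|
| Pain in the back or either leg | VAS at week 6 | VAS at weeks 12 and 24 | t-test on VAS change at secondary sites (Section VI) |
| Function of the injured ankle | FAAM at week 6 | FAAM at weeks 12 and 24 | t-test on FAAM change |
| Delayed healing | Week 6 assessment | Total treatment duration already recorded | None stated |
| Falls, new injury or re-injury, stopping boot or lift because of a problem | No survey item; recall at the week 6 visit | No stated route | None stated |

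The last row is the gap. A re-injury might lower a FAAM score, but the score would not identify the event or date it.

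**4. Why capture matters (illustration only).** Let r be the true proportion of lift patients with a given harm and c the proportion of such events that are recorded. Both are assumptions, since the documents give neither. With 50 lift patients:

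P(at least one recorded) = 1 − (1 − r·c)^50

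| r (assumed) | c = 1 | c = 0.5 (assumed) |
|---|---|---|
| 1% | 0.395 | 0.222 |
| 2% | 0.636 | 0.395 |
| 5% | 0.923 | 0.718 |
| 10% | 0.995 | 0.923 |

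For example, with r = 2% and c = 0.5: 1 − 0.99^50 = 0.395. Incomplete capture matters most for uncommon harms. For a harm affecting one patient in ten, at least one event would very likely be recorded even at half capture, although a count by arm would still be too low.

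**The case against.** The strongest reply is that much of the safety picture is already covered, and that part stands. Planned wear lasts six weeks and ends at a visit every patient attends. Extended treatment runs to later visits. The VAS covers the back and both legs, including the lifted side, at every time point, and the investigator reviews all outcome data. Treatment duration gives some signal of delayed healing. The lift is a low-risk item that patients can buy themselves.

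The text also leaves room for a wider reading. It does not say that visits are the only route, it does not define standard follow-up visits, and weeks 12 and 24 may be completed in person. But a wider reading of visits adds no question about non-pain harms and no comparison by arm.

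A reader might infer three stronger things that the documents do not support:

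- **That harms during wear will be missed.** They can be recorded at week 6. The weakness is dependence on recall, not certain loss.
- **That under-recording favours the lift.** The same route applies to both arms. It would hide a harm if the lift causes non-pain events, and a benefit if levelling the legs prevents them.
- **That simple figures measure the gap.** The share of follow-up after the last universal visit, (24 − 6)/24 = 75%, is mostly time after planned wear has ended. The rule-of-three limit for no events in 50 patients, 3/50 = 6%, is a property of the sample size, and better collection would not change it. Neither counts missed events.

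**Conclusion.** The point holds for non-pain harms. As written, the plan does not solicit them, relies on recall at week 6, states no route after week 6 for patients who have healed, and plans no tabulation by arm. They may be under-recorded, by an amount and in a direction that the documents do not allow anyone to state.

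This rests on two readings: that the surveys contain only the FAAM and the VAS, as Section V lists them, and that the later visits in Section V apply only to incomplete healing. The probabilities in the working rest further on assumed harm rates and an assumed capture of one half; they show how capture matters and do not estimate it.

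The primary comparison and the sample size are unaffected. This is a worthwhile, inexpensive improvement to safety data that a recommendation for the lift would otherwise lack.

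**What to change.** 1. Add the same short items to the REDCap surveys in both arms at weeks 6, 12 and 24: any fall, any new injury or re-injury, and any stopping of the boot or lift because of a problem, each with a date.
2. State a route by which patients can report such events between surveys. Items at week 6 alone would not let the alter-or-stop review act any sooner during wear.
3. Amend Section IX so that the principal investigator reviews these responses as they arrive as well as at visits, and say which contacts count as standard follow-up visits.
4. Keep sending the harm items to patients moved to alternative treatment for non-healing, who would otherwise drop out of view.
5. Add to Section VI a table of events by randomized arm.

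Rewording the Section VII statement on added risk as something the trial will assess is optional; the present text expresses an expectation and does not prevent harms from being recorded.

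The cost is slightly longer questionnaires and a little more review work. No clinic visits are added and the sample size does not change.
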